## 8.1 Methods and Procedures II:

**8.4** \* Please specify in detail the methods and procedures that are involved in this research.

Study Summary: This is a multi-site, placebo controlled, double-blinded RCT to confirm the superiority of PNS over PT in reducing HSP, and to determine if multimodal treatment of HSP with PNS + PT is more efficacious than PNS or PT alone. The standard of care for treating shoulder pain is to try several options, most commonly including medications, injections and therapy. Candidates considering this study likely have tried some treatments but without lasting success. Ninety-six participants will be randomized to receive PNS + PT, PNS + sham-PT, or sham-PNS + PT. The PNS + PT group will receive active PNS therapy for 6 hours per day for 3 weeks along with 8 sessions of PT to improve biomechanics of the affected shoulder. The PNS+ sham-PT group will receive active PNS therapy and sham-PT, consisting of placebo ultrasound, application of inert gel, lower limb strengthening, and walking exercises. The sham-PNS + PT group will receive a percutaneous lead in a similar manner as the active therapy groups, but with sham-stimulation, along with 8 sessions of PT. Measures of pain, pain interference with ADLs, QoL, shoulder biomechanics (shoulder abduction torque, shoulder kinematics, and Fugl-Meyer score), and measures of central sensitization (pain thresholds, secondary hyperalgesia, and temporal summation) will be assessed at baseline and at weeks 4 (end of treatment), 8, 12, 16, 20, 24, and 28.

Baseline Variables and Randomization: Baseline data will be collected so that the balance of covariates across the three groups can be evaluated. Each participant will be characterized with respect to demographics, comorbidities, and medication use. Study outcome measures (see Outcomes Assessment) will be administered to establish baseline levels. Participants are assigned to treatment groups using an adaptive randomization algorithm [90-92] to minimize group imbalances on key patient characteristics: baseline pain (>6 or <=6) [93], duration of pain (>=18 months or <18 months) [15], age (>=55 years or <55 years) and study site. For each assignment, the algorithm calculates the balance of these variables across the groups and makes an assignment that would result in greater balance in the variables across groups.

Check all that apply.

Check all that apply.

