Clinical Trials Cover Page: Study Protocol and Statistical Analysis Plan

Document Date: 11/5/2021

Multimodal Treatment for Hemiplegic Shoulder Pain

NCT02893267

Expectations and Analysis Compare the efficacy of PNS vs. PT in reducing HSP.

Hypothesis 1. The reduction in HSP will be greater in PNS alone vs. PT alone. Based on Preliminary Studies 1 and 2, an average reduction of 5 points (63%, assuming baseline of 8) in BPI SF-3 is anticipated for the PNS+shamPT group by EOT with maintenance of this effect at follow-up (Figure 7). Based on Preliminary Study 2, a 34% reduction is anticipated by the end of treatment for PT+shamPNS group, increasing to a 20% decrease by the end of follow-up. We anticipate an 87.5% reduction, or 2-points more than PT +shamPNS, by end of treatment for the PNS+PT group, maintaining this level at the end of follow up. The anticipated difference of at least 2.0 points between groups at 28-wks is the minimum clinically important difference in pain scores.152 153 In order to detect this difference with 80% power, α =0.05 (combined), and anticipated SD of 2.4, the minimum sample size is 27/group is necessary when using a one-sided, two-sample, equal-variance t-test of 3 pairwise comparisons (assuming pain reduction with PNS + PT >

[figure not shown]

Figure 7: Anticipated average BPI SF-3 trajectories for participants assigned to PNS+PT (dashed, diamond) PNS+shamPT(solid, triangle), and PT+shamPNS (dotted, square). Shaded area indicates treatment.

PNS+shamPT > PT + shamPNS). With the anticipated drop-out rate of 20%, this leads to a sample size of 32/group for a total of 96 participants.

Exploratory looks at the data across the three groups are done first before fitting our models. Poolability of data across sites will be evaluated and adjusted for as needed. Comparability of demographics by site will be assessed. Treatment by site interaction will be tested. Each measure will be modeled using a linear mixed effects approach which is well-suited for handling correlated repeated measurements, unbalanced data, missing data and dropouts in longitudinal studies. These mixed effects models yield estimates of the treatment, time and treatment by time while permitting us to control for potential confounders. Analysis for comparison of responders will be completed with logistic regression analysis with treatment group as independent variable.

AIM 2. Compare the efficacy of PNS + PT, PNS + ShamPT, and PT + ShamPNS in reducing HSP.

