Hypothesis 2. The reduction in HSP will be the greatest with PNS + PT, followed by PNS + Sham PT, and finally PT + Sham PNS. Continuous data will be analyzed using the approach described for hypotheses 1. As a phase II trial, power analysis was conducted only for the primary outcome measure (Worst Pain in the Last Week, BPI SF-3).

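### The efficacy model commits to none of the four minimisation factors and leaves the role of baseline BPI SF-3 unstated; naming these terms in advance costs only SAP wording

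*SAP*

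**What the plan says.** Protocol item 8.4 (Baseline Variables and Randomization) describes an adaptive algorithm that balances the three groups on "baseline pain (>6 or <=6) [93], duration of pain (>=18 months or <18 months) [15], age (>=55 years or <55 years) and study site". It gives the purpose of collecting baseline data as a balance check: "Baseline data will be collected so that the balance of covariates across the three groups can be evaluated". The study summary in the same item lists baseline with the follow-up assessments: outcomes "will be assessed at baseline and at weeks 4 (end of treatment), 8, 12, 16, 20, 24, and 28".

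The SAP (Expectations and Analysis) models each measure with linear mixed effects. It names three terms and leaves the rest open: "These mixed effects models yield estimates of the treatment, time and treatment by time while permitting us to control for potential confounders". On site it says: "Poolability of data across sites will be evaluated and adjusted for as needed". A treatment-by-site test is planned, with no stated consequence for the efficacy model. Before modelling, "Exploratory looks at the data across the three groups are done first before fitting our models". Aim 2 inherits this: "Continuous data will be analyzed using the approach described for hypotheses 1".

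The sample size rests on a test without covariates: "anticipated SD of 2.4, the minimum sample size is 27/group is necessary when using a one-sided, two-sample, equal-variance t-test of 3 pairwise comparisons". The SAP does not say whether 2.4 is the SD of the week-28 score, of the change, or of a residual.

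**The concern.** Two statisticians could follow this text faithfully and fit different primary models. One could leave baseline pain out, one could treat it as the first repeated response, and one could adjust for it. These models differ in power, and the documents do not give the correlation that decides between them.

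The covariate set is open too. For site, adjustment is explicitly data-dependent. For the other factors the SAP does not say they will be chosen from the data, but it does not exclude it: covariate balance is to be evaluated, and looks across groups come before model fitting.

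Minimisation does not replace adjustment for baseline pain. It balances only a cut at 6, whereas entry requires a score of at least 4 (Protocol 9.1) and the SAP assumes a mean near 8. Most patients probably fall above the cut, where the score can still vary between groups.

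**Working it through.** **Inputs from the documents.** Difference 2.0 points at week 28; SD 2.4; one-sided 0.05 shared over three comparisons; 27 per group; 20% drop-out; 96 randomised; assessments at baseline and weeks 4 to 28 (SAP; Protocol 8.4).

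**Assumed, because the documents do not give them.** Baseline-outcome correlation r from 0 to 0.6; baseline SD 1.44 (1.2 and 1.8 also tried); share of variance explained by duration, age and site 0 or 10%; site split 50/30/20; residual correlation between visits 0.6 (0.8 also tried).

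**1. The plan's own figure.** Noncentrality = 2.0 / (2.4 × √(2/27)) = 3.06 on 52 df. At one-sided 0.05/3 = 0.0167 the power is 80.7%, and 26 per group gives 79.0%. So 27 per group reproduces as an unadjusted t-test.

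**2. Closed form, completers.** 96 × 0.8 = 76.8, about 77, or 25.7 per group. With 2.4 as the SD of the score:

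- final score: SD = 2.4
- change score: SD = √(2.4² + 1.44² − 2·r·2.4·1.44)
- baseline-adjusted: SD = 2.4·√(1 − r²)

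| r | change SD | adjusted SD | power: final | change | adjusted |
|---|---|---|---|---|---|
| 0.1 | 2.673 | 2.388 | 78.5% | 68.8% | 78.9% |
| 0.3 | 2.400 | 2.289 | 78.5% | 78.5% | 82.3% |
| 0.5 | 2.092 | 2.078 | 78.5% | 88.8% | 89.2% |

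Below r = 1.44 / (2 × 2.4) = 0.3 the change score is the worse unadjusted choice; above it the final score is.

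**3. The other readings of 2.4 (same formulas, baseline SD 1.44, r = 0.1 / 0.3 / 0.5).**

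- SD of change: change score 78.5% throughout; final score 89.5 / 78.5 / 65.5%; adjusted 89.8 / 82.3 / 78.5%.
- Residual SD: adjusted about 78.5% throughout, because the gain is already counted; final score 78.0 / 74.3 / 65.5%.

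Across the three baseline SDs, r from 0 to 0.6 and all three readings, and allowing for the cost of estimating the slope, adjusted power is at most 0.7 points below the better unadjusted contrast.

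**4. Mixed model as planned.** Simulation with deterministic minimisation of 96 patients to three arms on the four factors; integer baseline scores 4 to 10 (mean 7.9, 82.8% above 6); unstructured covariance; drop-out missing at random after week 4; week-28 contrast. With no effect of duration, age or site:

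| r | baseline omitted | first repeated response | continuous covariate |
|---|---|---|---|
| 0 | 83.5% | 72.8% | 83.2% |
| 0.1 | 83.6% | 76.6% | 83.6% |
| 0.3 | 84.3% | 84.4% | 86.7% |
| 0.5 | 85.9% | 92.4% | 92.4% |

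With residual correlation 0.8 the pattern is the same: 86.4 / 86.3 / 88.6% at r = 0.3 and 87.6 / 93.8 / 93.9% at r = 0.5.

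Adding duration, age and site costs 0.1 to 0.3 points if they have no effect. It gains 1.5 to 2.3 points if they jointly explain 10% of the variance.

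**5. Type I error (nominal 1.67%).** With baseline omitted, at r = 0.1 / 0.3 / 0.5: 1.68 / 1.52 / 1.24% without factor effects, and 1.29 / 1.17 / 0.87% with the assumed 10%. With all four terms in the model it is 1.68 to 1.74% throughout.

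**The case against.** The best case for the plan is that its wording points to baseline as the first repeated response. The hypotheses concern reduction, treatment by time is a named estimate, and baseline is listed with the other assessments. On that reading adjustment gains 2.3 points at r = 0.3 and nothing at 0.5. The large gains need r of 0.1 or less, which sits oddly beside a residual correlation of 0.6 between follow-up visits. In the mixed model, only first response at r of 0.1 or less falls below the planned 80%. Omitting the factors does no harm to validity, site is partly handled, and every power figure depends on assumed inputs.

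Much of this stands. The gain may be small, and the figures show direction and range only. But the SAP does not state the first-response reading, and even if it did, adjustment would cost almost nothing where it does not help.

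Dates carry little weight. The SAP cover date (11/5/2021) is later than the anticipated end (5/31/2021, CRU Application item 1.05), but it may date the posting: Protocol 10.4 lists an analysis attachment under the same heading and a revised sample-size file from 2016. The documents do not give unblinding status.

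Questionnaires are also administered at Visit 3, so a second pre-stimulation value exists. Visit 2 is the labelled baseline assessment, and the SAP should say so. The responder logistic regression, which names treatment group only, has the same gap.

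**Conclusion.** The concern holds. Allocation uses four factors; the efficacy model commits to none, and the role of baseline BPI SF-3 is not stated. This is a matter of efficiency and of an open analysis choice, not of inflated error.

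With 2.4 as the SD of the score and baseline SD 1.44, the covariate gains −0.3 to 6.5 points of power over omission and 0 to 10.4 over first response, for r from 0 to 0.5. Which alternative it beats depends on r; it is close to the better one or above it in every case tried. The gain comes from continuous baseline pain. Duration, age and site help only if they are prognostic. The plan should be changed, with medium confidence in the size of the benefit.

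**What to change.** Pre-specify the primary mixed model:

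- **Response:** BPI SF-3 at weeks 4, 8, 12, 16, 20, 24 and 28.
- **Fixed terms:** treatment, time, treatment by time, continuous Visit 2 BPI SF-3, baseline by time, site, pain duration (≥18 vs <18 months) and age (≥55 vs <55 years), all kept whatever the poolability result.
- **Treatment by site:** keep as a descriptive check.
- **Other continuous outcomes:** use each outcome's own baseline in the same way.
- **Sample size:** state what the SD of 2.4 describes.
- **Timing:** if group data have already been examined, state when the covariates were fixed.

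The cost is SAP wording and about five degrees of freedom (baseline, duration and age one each, site two), plus 7 − 1 = 6 for baseline by time. No visits, data or patients are added. It would be consistent to name covariates for the responder model at the same time.
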